## 10.5. Secondary Analyses

We will describe the rates of completion of the health status outcome reporting the five items from the EQ5D using frequencies and proportions. The total EQ5D score will be reported at each time point (baseline, 3 and 6 months) using means (SD), or median (IQR) as appropriate. The modelling approach for EQ5D total score will follow the same approach using a mixed-effects generalised linear model. The outcome measure, total EQ5D score at 3 and 6 months follow-up, will be assumed to be normally distributed, and a mixed-effects generalised linear model will be fitted with the assumption of normality( $F$ ) $\eta$  including fixed-effects for the baseline EQ5D score, interactions of intervention arms and time points (3 or 6 months follow-up) and LAs RSI funding allocation 2022-2025 strata, and a random effect for the Local Authority. The model fit will be assessed using appropriate statistics including residuals, in case of any departure from the model assumptions, an alternative method of modelling such as Generalised Estimating Equation (GEE) will be explored. A similar approach of analysis will be taken with the EQ VAS score (between 0='The worst health you can imagine' and 100='The best health you can imagine').

## 10.6. Sub-group Analysis

In a full scale RCT, analyses of a difference in treatment effect for subgroups might provide useful information. However, such analyses in a pilot trial are not applicable because the primary focus is not on determining treatment effects or differences in effects between subgroups.

## 10.7. Sensitivity Analysis

We will examine the balance of covariates (baseline demographics or factors associated with intervention and outcome) by arm and decide whether adjustment is required, and if so, perform as a separate sensitivity analysis to check for movements in the estimated effects.

## 10.8. Missing Data

We will estimate the proportion of missing data for all covariates and outcomes. The patterning and percentage of missing data will inform the likely analytical strategy in a full-scale effectiveness trial. Using CHI guidance, if more than 5% of any variable (covariates and outcomes) is missing then we will examine whether those missing are conditional on covariates (e.g. age (years), sex, nationality, care experienced, left an institution in the last 85 days) or outcome data using logistic regression (to predict missingness). We will also use visualisation of missing data by using the R-package VIM (Templ, 2008). No imputation will be performed in this current pilot study.

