**Table 8: Feasibility Criterion**

Feasibility Criterion	Red	Amber	Green
Trial methods			
1. Successful recruitment and randomisation of 16 Local Authorities	<10	10-15	16
2. 12 Local Authorities remain in the pilot study	<10	10-11	≥12
3. Data is collected for more than 60% of service users at baseline and the final follow-up on primary outcome	<50%	50-60%	>60%
Intervention			
4. The intervention being delivered with fidelity	Low	Medium	High
5. The intervention is acceptable to service users, Local Authority staff, and nurses	Low	Medium	High

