### 10.4. Primary Analysis

The rate of completion of the primary outcome - housing situation via the RTLFB inventory will be reported at each follow-up time point (baseline, 3 and 6 months). In service users providing valid data, we will summarise their housing situation using frequencies and proportions in three ways:

- Level 1: Categorical outcome – homeless, not homeless, institution
- Level 2: Categorical outcome – rough sleeping, temporary and/or unstable, hidden, institution, stable but insecure, stable and secure
- Level 3: Categorical outcome - all twelve categories (A1 to E12)

See Appendix C for the coding of the outcomes.

If a service user reports to be in an institution (e.g. prison, probation facility, hospital or asylum support accommodation) at the time of follow-up, they are neither defined as homeless or not homeless. For this reason, we will use the additional definition of homelessness developed by RTLFB Inventory of 'functional homelessness'. The RTLFB Inventory developed rules that detailed when an institutional setting would be considered functional homelessness e.g., a psychiatric hospitalisation (institutional setting) would not be considered functionally homeless if a service user was living in a stable setting (i.e. not homeless) prior to the hospitalisation and returned there once discharged. However, if the service user was rough sleeping prior to hospitalisation and returned to the street upon discharge, then they would be considered functionally homeless for that entire duration. For this reason, if a service user reports to be in an institution at the time of follow-up we will take their previous housing situation for the purpose of the analysis; this will be used for of all levels of categorisation.

The primary analysis will use a multilevel (two levels) mixed-effects generalised linear modelling technique to examine the intervention effect on Level 2 categorisation of housing situation at 6 months.

The model will contain the trial arm as a main fixed effect, will adjust for LAs RSI funding allocation 2022-2025, and will account for the nesting (random-effect) of service users within LA, resulting in observations within the same cluster likely to be correlated (ignoring this can lead to underestimated standard errors and overstated statistical significance). We will not adjust for baseline measure as all service users will be rough sleeping. A general equation of

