the multilevel mixed-effects generalised linear model for our analysis can be described as follows:

$$g(y|X, u) = X\beta + Zu + \varepsilon$$

The fitted model can be formulated as bellow:

$$g\{E(y|X, u)\} = X\beta + Zu$$

where:

- $y \sim F$  (i.e., the outcome  $y$  follows a distribution  $F$  (e.g., normal, binomial, ordinal etc.))
- $y$  is the ( $n \times 1$ ) vector of responses from the distribution  $F$  such as for the outcome level 1, it takes values as (1=stable but secure), (2=stable but insecure), (3=hidden, temporary and/or unstable), (4=rough sleeping).
- $X\beta + Zu = \eta$  is called a linear predictor and its terms are described as below:
- $X$  is an ( $n \times p$ ) design/covariate matrix for the fixed effects  $\beta$  including the study arms (intervention=1 versus control=0) and LAs RSI funding allocation 2022-2025 strata (e.g., 0=low RSI funding allocation, 1=high RSI funding allocation) and other baseline covariates such as service users' age and gender.
- $Z$  is the ( $n \times q$ ) design/covariate matrix for the random effects  $u$  assumed to be normally distributed with mean 0 and ( $q \times q$ ) variance matrix ( $\Sigma$ ). In this study, it may be kept limited to the random effect of local authority (clusters) only matrix  $\Sigma$ .

The effect size will be reported as an absolute risk differences (intervention minus control) alongside 95% CIs, at each time point. Adjusted relative risk ratios for intervention versus control will be computed from the model presented alongside 95% CI. We will also estimate the clustering of outcomes by trial arm via intra-cluster correlation coefficients (with 95% CIs). The effect estimates will be used for the sample size calculation of a future definitive study.

For analysis of the Level 1 outcome, the outcome will be a binary outcome (homeless=0 vs not homeless=1) and a mixed effect logistic regression model, with the assumption of binomial distribution, will be used to compute the point estimate as relative risk ratios alongside 95% CI.

For the categorical (ordinal) outcome of Level 3 all twelve categories (A1 to E12) will be included. The mixed-effects generalised linear model will be fitted with the assumption of ordinal distribution, a logistic link function and a suitable linear predictor  $\eta$  including a random effect of the Local Authority. In all analyses, model assumption will be evaluated to insure a best fit of the model.

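### Section 10.8 examines missingness by logistic regression on service-user covariates with no Local Authority term, so differences between Local Authorities can be misread as service-user predictors of missing data

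*Protocol*

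**What the plan says.** Protocol section 10.8 sets a trigger, "if more than 5% of any variable (covariates and outcomes) is missing", and then examines whether missingness depends on covariates "or outcome data using logistic regression (to predict missingness"). The covariates offered as examples are "e.g. age (years), sex, nationality, care experienced, left an institution in the last 85 days". LA, trial arm and the funding stratum are not among them. The section also says "No imputation will be performed in this current pilot study", and gives the purpose of the exercise: "The patterning and percentage of missing data will inform the likely analytical strategy in a full-scale effectiveness trial".

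The outcome models are written differently. For the Level 1 housing outcome, section 10.4 states that "a mixed effect logistic regression model, with the assumption of binomial distribution, will be used". Section 10.4 also puts an LA random effect in the primary and Level 3 models, and section 10.5 does so for EQ-5D. Of the nesting of service users within LAs, section 10.4 warns that "ignoring this can lead to underestimated standard errors and overstated statistical significance".

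On loss of LAs, Table 8 (section 7.1) has the criterion "2. 12 Local Authorities remain in the pilot study", rated green at 12 or more of the 16. The withdrawal procedure in Appendix A foresees an LA that leaves both the trial and its follow-up.

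**The concern.** Whether a service user is found at 3 or 6 months depends partly on the site. Under section 8.1, follow-up in intervention sites is collected mainly by the nurse working there. In control sites a shared team member from the delivery partner supports it and helps the local teams. Section 8.1 also treats withdrawal of an LA over data-collection problems as a serious threat. When an LA withdraws fully, all its later outcomes are missing for a reason that has nothing to do with any individual's characteristics.

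A logistic regression without an LA term treats 640 service users as independent. If nationality, say, is distributed unevenly across LAs, and the LAs that lose data happen to have an unusual mix, nationality will look like a predictor of missingness, with an interval that is too narrow.

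Learning about missing data is a main product of this pilot: research questions 4.2 and 4.3, feasibility criterion 3, and the attrition objective in section 9.2. A full-scale trial planned on a misread pattern could build its missing-data model on covariates that do not drive the loss.

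**Working it through.** **Inputs from the protocol.** 16 LAs, average 40 service users each, outcome ICC 0.10 (section 9.1, Table 10); up to 4 of 16 LAs lost and still green (Table 8).

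**Inputs assumed.** Missingness ICC 0.10 (set equal to the outcome ICC); covariate ICC 0, 0.10 or 0.20; individual missingness of 20% or 30% in LAs that stay. The protocol gives none of these.

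**The plan's own figures first.** Design effect 1 + (40 − 1) × 0.10 = 4.9. Effective number per arm 320/4.9 = 65.3. Detectable effect with 14 degrees of freedom: (t0.975 + t0.80) × √(2/65.3) = 0.527, which matches 0.53. Attrition: 640/0.9 = 711.1, which matches 711. The cluster structure used below is therefore the plan's own.

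**Approximation for the missingness model.** For a service-user covariate with ICC ρx and missingness with ICC ρy, the variance that ignores LA is too small by about

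D = 1 + (40 − 1) × ρx × ρy.

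A nominal 95% interval for a covariate with no effect then excludes 1 with probability 2 × [1 − Φ(1.96/√D)].

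*No LA lost (ρy = 0.10):*

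| Covariate ICC | D | √D | Interval excludes 1 |
|---|---|---|---|
| 0 | 1.00 | 1.00 | 5.0% |
| 0.10 | 1.39 | 1.18 | 9.6% |
| 0.20 | 1.78 | 1.33 | 14.2% |

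*Four LAs wholly lost.* Losing whole LAs raises the missingness ICC sharply. With individual missingness q in the other 12:

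- Overall missingness p = 0.25 + 0.75q.
- Between-LA variance = 0.25 × 0.75 × (1 − q)² + 0.75 × 0.10 × q(1 − q).
- ρy = between-LA variance / [p(1 − p)].

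For q = 0.20: p = 0.40, ρy = 0.132/0.240 = 0.55. For q = 0.30: p = 0.475, ρy = 0.1076/0.2494 = 0.43.

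| Covariate ICC | D (q = 0.30 / 0.20) | Interval excludes 1 |
|---|---|---|
| 0 | 1.00 / 1.00 | 5% / 5% |
| 0.10 | 2.68 / 3.15 | 23% / 27% |
| 0.20 | 4.37 / 5.29 | 35% / 39% |

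**Simulation check** (16 LAs of 40; binary and continuous covariates with no true effect; missingness ICC 0.10). Ordinary logistic regression excluded 1 in:

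- No LA lost: about 4–6% at covariate ICC 0, 8–10% at 0.10, 13–14% at 0.20.
- Four LAs lost: about 5% at covariate ICC 0, 23–27% at 0.10, 34–40% at 0.20.

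The mean log odds ratio, recorded for the continuous covariate, was about 0 in every setting. Across trials the fault is therefore over-narrow intervals, not bias in one direction; in any single trial it shows as a spurious association.

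**With LA accounted for.** Stratifying by LA gave 4.8–5.5%, and LA fixed effects gave about 4–7%. A random LA intercept gave about 4–6%, but about 10% at covariate ICC 0.20 when wholly lost LAs were kept in the model. That exception is the reason to fit the model only among LAs still in follow-up.

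**The case against.** The strongest reply is that section 10.8 never says single-level. Its covariate list is open, section 10 calls itself a brief overview, and a detailed SAP is promised that could add an LA term. This stands in part: a reader might infer that the protocol prescribes a model ignoring LA, but that rests on the wording and on the contrast with 10.4 and 10.5. It does not remove the point. Section 10.8 names a method and a type of predictor, and following it as written departs from the protocol's own warning about nesting.

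Other stronger readings also go beyond the documents:

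- *That LA differences will appear as service-user predictors.* They can. It needs a covariate whose mix differs between LAs, and the protocol has no figures on that.
- *That missingness is at least as clustered as housing because each LA's own staff collect the data.* Section 8.1 does not support this. Follow-up relies largely on the delivery partner's nurses and, in control sites, on one team member shared across sites, which could weaken clustering.
- *That loss of whole LAs would go unnoticed.* LA withdrawals appear in the CONSORT diagram (10.2), LA retention is research question 3.2 and feasibility criterion 2, and withdrawing LAs are to be interviewed (11.2.1). Reasons for non-contact are also recorded (Table 9).
- *That a lost LA is always 100% missing.* Appendix A keeps following its service users unless the LA withdraws fully, and Table 10 expects no cluster attrition. The four-LA figures are the extreme that criterion 2 still rates green.
- *That the trial result is distorted.* With no imputation, the missingness model does not feed the effect estimate.

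Section 10.10 rules out p-values. That does not settle the matter, because judging whether missingness depends on a covariate still rests on an interval that is too narrow.

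**Conclusion.** The point holds as a limited but worthwhile correction. As written, section 10.8 leaves LA out of the missingness model, although LA is in every outcome model that the protocol spells out. If LA is ignored, a covariate with no effect has a 95% interval excluding 1 in about 8–14% of trials with no LA lost, and in about 24–40% with four LAs wholly lost, against a nominal 5%. These figures assume a missingness ICC of 0.10 and a covariate ICC of 0.10 to 0.20, with 20–30% individual missingness in the four-LA case. At covariate ICC 0 the excess disappears. The consequence is confined to what the pilot teaches about the causes of missing data; the housing and health effect estimates are not affected.

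**What to change.** In section 10.8 or the SAP:

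1. Tabulate missingness of each outcome by LA and by arm.
2. Report service users lost through full withdrawal of their LA separately from those lost individually.
3. Fit the missingness model among LAs still in follow-up, with LA accounted for by a random intercept or by stratification. The random intercept follows the form already used for the Level 1 outcome. Stratification cannot estimate an effect of arm, because arm is constant within an LA, so the table in step 1 would have to show that.

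This takes a few sentences and needs no new data. The cost is wider intervals for covariates that vary between LAs.

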## **10.9. Interim Analyses**

There are no interim analyses to be performed.

## **10.10. Adjustment of Confidence Intervals and p-values for Multiple Statistical Tests**

As a pilot, our analyses are exploratory rather than confirmatory; no statistical testing will be performed, and no p-values will be reported. Therefore, no adjustment for multiplicity will be undertaken.

## **11. IMPLEMENTATION AND PROCESS EVALUATION (IPE)**

### **11.1. Aim, Objectives and Research Questions**

#### **11.1.1. Aim and objectives**

The implementation and process evaluation (IPE) aims to collect data to understand how the outreach with a health specialism intervention is implemented, whether the hypothesised mechanisms of action are activated, and how contextual aspects impact on outcomes. Data will be collected to address specific research questions developed for the IPE as well as to provide interpretation and depth of understanding of trial data on primary and secondary outcomes.

The objectives are:

- To explore whether the intervention is delivered as intended and is reflective of the training content
- To examine whether the mechanisms of change identified in the programme theory operate as theorised and whether other mechanisms exist
- To explore acceptability and viability of the intervention and examine perceived impacts of the intervention from the perspectives of staff and service users
- To provide data for interpretation of trial outcomes
- To explore the feasibility and acceptability of main trial processes

#### **11.1.2. Research questions**

The research questions for the IPE reflect MRC Process Evaluation guidance on key domains (Moore, 2015) and have been developed to explore: fidelity; reach; acceptability; context; mechanisms of change; differentiation from usual care; perceived outcomes and trial processes.

RQ1 Is the intervention delivered with fidelity?

- 1.1 Does the intervention content reflect the training received by outreach nurses?
- 1.2 What adaptations to intervention content are made and how do these impact delivery as intended?
- 1.3 Are outreach nurses able to spend the intended time on intervention activities?

RQ2 Does the intervention reach the intended target population of people rough sleeping?

RQ3 Is the intervention acceptable to service users, other professionals, and nurses?

- 3.1 What do the nurses think about the intervention components, and what gaps in the provision have been identified?
- 3.2 How do service users perceive the intervention components received and what gaps in provision are identified?
- 3.3 Do other professionals interact with the service and work effectively with outreach nurses, including integration with existing teams?
- 3.4 Does the lead nurse supervision operate as intended and it is acceptable to outreach nurses?

RQ4 How do context factors impact intervention delivery?

- 4.1 How do variations in time of day, length of shift and local geographical factors influence intervention delivery?
- 4.2 How does the availability of local services (housing and health) impact intervention outcomes?
- 4.3 How do variations in local data sharing processes, professional structures and collaborative relationships impact intervention delivery and outcomes?

RQ5 What evidence is there for the mechanisms of change as identified in the intervention logic model and does the evidence suggest revisions to this model?

- 5.1 Does the outreach nurse role represent 'fresh' engagement for outreach teams, creating opportunities to have new and reframed conversations around housing and other social care needs and what are the outcomes of this?
- 5.2 Does outreach nurses' professional credibility increase engagement with both service users and outreach services related to housing? If so, how?
- 5.3 Does the clinical expertise of outreach nurses increase clients' confidence in, and uptake of, health, social care, and housing services? If so, how?
- 5.4 Are outreach nurses able to provide clinical and legal advocacy for service users and is this effective?
- 5.5 Does inter-professional recognition between outreach nurses and other health professionals improve quality of related care assessments? If so, how?
- 5.6 Does the outreach nurse role increase the number of people identified as having a valid pathway to accommodation entitlement based on a significant health need and what are the outcomes of this?
- 5.7 How do outreach nurses pre-existing experiences and inter-personal skills act as barriers/facilitators to intervention delivery?
- 5.8 What other mechanisms of change are evident?

RQ6 To what extent can the intervention be differentiated from existing outreach provision?

6.1 Is it possible to accurately describe treatment as usual in control sites and the differences from intervention content?

RQ7 What are the perceived outcomes of the outreach with a health specialism intervention on those receiving the service?

7.1 What housing and health needs are met/unmet by the intervention?

RQ8 Are trial methods feasible and acceptable?

8.1 Is randomisation acceptable to LAs and why/why not?

8.2 Are there any potential ethical, practical, statutory, or other legal barriers that impact recruitment and retention of LAs and randomisation processes?

8.3 Are methods of data collection feasible and what refinements (if any) are needed?

8.4 Are the target population (people rough sleeping) recruited and retained effectively?

## **11.2. Research Design and Methods**

### **11.2.1. Overview**

The embedded IPE will adopt a mixed methodology, drawing on routinely collected contextual data, and qualitative interviews aimed at understanding lived experience of those delivering and receiving the service. We will purposively sample seven sites (five intervention and two usual care control sites). We will also interview LA representatives should any site withdrawals be received.

Within each sampled intervention and control site we will conduct semi-structured interviews with two staff members. These will be conducted by telephone (or online, depending on staff interviewee preference). We will also conduct in-person, semi-structured interviews with three service users (n=21) in these sites. Site staff will support us in identifying key characteristics to include in sampling service users for interviews with the aim of recruiting a varied sample in terms of sex, age, ethnicity, and other key factors identified across the whole sample.

At each sampled site, the researcher will also conduct two observations of intervention delivery and will complete a checklist and field notes. Observations will reflect the main study aims and will 1) Explore how the organisational and geographic context influences the delivery of the outreach service within the Local Authority; 2) Explore the fidelity of the intervention within the Local Authority and differences with usual care.

A time and resource logbook proforma will be completed by staff delivering the service.

Finally, we will interview a key member of staff in each LA that opts to withdraw from the study (potential maximum of 8 interviews). Again, these will be conducted by telephone (or online, depending on staff interviewee preference).

